STEMI assessed as the presence of electrocardiographic (ECG) and biomarker criteria for acute myocardial infarction within 48 h of the index arrest.⁽¹²⁸⁾ Note that ST-elevation on the first 12-lead ECG after resuscitation is a poor predictor of acute infarction in this population.⁽¹²⁹⁾ These patients often develop infarctions during the subsequent 48 h.

Myocardial Injury assessed as peak serum troponin in ng/mL at any time point within 24 h of index arrest.

Renal Dysfunction assessed using Risk, Injury, Failure, Loss, End Stage criteria.^(130, 131)

Hospital Free Survival (HFS) assessed as number of days alive and permanently out of hospital up to 30 days post arrest. Patients who die before discharge will be assigned zero days out of hospital. Note that other randomized trials that enrolled patients with cardiac arrest have described similar outcomes such as days on a ventilator, in an intensive care unit or in hospital.^(31, 132, 133) However such assessments were potentially limited because they did not account for the differential timing of mortality. Importantly, HFS has been used as an outcome in trials in patients with heart failure,^(134, 135) renal failure,⁽¹³⁶⁾ cancer,⁽¹³⁷⁾ or need for intensive care.⁽¹³⁸⁾ As well, HFS is recommended as an outcome in trials that enroll patients with need for intensive care.⁽¹³⁹⁾ The description of HFS will provide additional granularity to our results.

Withdrawal of Care assessed as the reduction of support (i.e. reducing pressors, lab draws or medications) or withdrawal of support (i.e. extubation, stopping drips/meds, changing to comfort care only) during hospitalization.

Favourable Neurologic Status at Discharge assessed using modified Rankin Score (MRS) ≤ 3 at hospital discharge or 30 days after index arrest.

Survival to Discharge assessed as alive when discharged from hospital to home, nursing facility or rehabilitation. Patients transferred to another acute care facility (e.g. to undergo implantable defibrillator placement) will be considered still hospitalized.

Clinical Instability at Discharge assessed using the Kosecoff Index⁽¹⁴⁰⁾ measured at discharge based on the presence of nine symptoms and signs associated with increased risk of rehospitalization. Instability will be the presence of any of these.

Survival to 30 Days After Cardiac Arrest assessed as alive 30 days after the index cardiac arrest as confirmed by a brief telephone interview. Note that some experts suggested that the primary outcome of trials in patients with OHCA should be assessed 90 days after discharge.⁽¹⁴¹⁾ However, we showed that such post-discharge scores were well correlated with assessments before discharge.⁽¹⁴²⁾ As well, post-discharge assessment was susceptible to informative missingness as the characteristics of those who consented for follow up were different from those who did not. Lyden and colleagues made similar observations about short vs. long-term outcomes after stroke.⁽¹⁴³⁾ Importantly, post discharge assessments burden patients and prolong study duration. We will confine post-discharge assessment to a brief telephone interview at 30 days.

Accrual is the proportion of eligible subjects who have the study device applied.

SAFETY OUTCOMES

Expected Adverse Events

Device Failure Malfunctions are unlikely due to the simple construction and durable materials of the devices. However, device failure will be defined as discontinuation of use of the device prior to the end of allocated treatment interval because of mechanical failure as opposed to provider preference.

Related to Device RIC is generally well-tolerated, but several side effects will be monitored. Most important are pain at the site of application, or thrombophlebitis, or infection.

Pain assessed using the Richmond Agitation-Sedation Scale at 30 and 60 minutes after randomization in control and intervention group patients.^(144, 145) No gold standard exists for pain assessment in sedated and ventilated patients.⁽¹⁴⁶⁾

Thrombophlebitis assessed as symptomatic non central nervous system venous or arterial thrombus documented radiographically or ultrasonographically.

Sepsis assessed within one week of index arrest as either i) the presence of microbiologically proven, clinically proven, or suspected infection; or ii) presence of Systemic Inflammatory Response Syndrome (SIRS); and iii) development of at least one organ dysfunction within the preceding 24 hours.⁽¹⁴⁷⁾

Related to Cardiac Arrest The following are commonly observed in patients who experience cardiac arrest, and may or may not be attributable to specific resuscitation therapies. These will be monitored and reported but not classified as serious adverse events. Clinical diagnoses of pneumonia, cerebral bleeding, stroke, seizures, bleeding requiring transfusion or surgical intervention, rearrest, pulmonary edema, serious rib fractures, sternal fractures, internal thoracic or abdominal injuries as noted in the hospital discharge summary.

Unexpected Adverse Events (UAE)

These will be defined as any serious unexpected adverse effect on health or safety or any unexpected life-threatening problem caused by, or associated with, a device, if that effect or problem was not previously identified in nature, severity, or degree of incidence in the investigation plan or application, or any other unexpected serious problem associated with a device that relates to the rights, safety or welfare of subjects. Death or neurological impairment will not be considered an adverse event in this study, as it is an expected part of the natural history of the illness for a large proportion of the population.

Covariates Key covariates of interest include but are not limited to:

Initial rhythm: (i) VF, vs. (ii) PEA, vs. (iii) asystole, vs. (iv) unknown.

Observational status of arrest:⁽¹⁴⁸⁾ (i) witnessed by EMS, vs. (ii) witnessed by bystanders, vs. (iii) unwitnessed;

Bystander CPR status:⁽¹⁴⁹⁾ (i) performed, vs. (ii) not performed, vs. (iii) unknown.

Response time interval from call to initiation of CPR by EMS:⁽¹⁵⁰⁾ among witnessed cardiac arrests grouped as (i) < 10 minutes, vs. (ii) ≥ 10 minutes.

Gender:⁽¹⁵¹⁾ (i) male vs. (ii) female.

Strata of initial depth of coma:⁽¹²⁴⁾ based on FOUR score.

Strata of initial cardiopulmonary dysfunction:⁽¹²⁵⁻¹²⁷⁾ based on SOFA score.

ANALYSES

Interim Analyses

The data will be monitored regularly by an independent data safety monitoring board (DSMB) to ensure study integrity and patient safety.

Monitoring of Study Conduct

The timeliness, completeness, and accuracy of data entry will be analyzed continuously, with reports provided monthly to the Study Executive Committee. This information will be provided in periodic reports to the DSMB.

Analyses

All outcomes will be summarized descriptively, without statistical comparison as recommended for pilot studies. No claims will be made based on the results of this trial.

ANALYSIS POPULATIONS

Safety Population

This will include all randomized patients, regardless of initial rhythm and duration of exposure to RIC. Patients will be analyzed within their assigned treatment arm, thereby using an intent-to-treat strategy. This is appropriate given that there are no controlled prior data related to RIC in patients with OHCA. Therefore, we are interested in testing the safety of RIC.

Efficacy Population

This will include all randomized patients whose initial rhythm was VF, regardless of duration of exposure to RIC. Patients will be analyzed within their assigned treatment arm, thereby using a modified intent-to-treat strategy. Note that rhythm is a pre-randomization variable.

SAMPLE SIZE

The null hypothesis is that the attrition rate will be not more than 25%. We assume 59 patients are treated by EMS providers for OHCA (21 due to VF) and have spontaneous circulation upon arrival at the participating receiving hospital annually. We will enroll 30 patients (15 per group) as recommended for pilot studies.⁽¹⁵²⁾ These numbers will allow estimation of accrual with precision (as measured by half-width of 95% CI) of at least 16.8% overall (and 23.7% within each group).

SAFETY AND DATA MONITORING PLAN

Clinical staff will report potential adverse events as soon as possible. The DSMB will review and approve the protocol before the study begins, evaluate rates of outcomes and adverse events throughout the study period, and determine the final monitoring plan. We will forward reports of DSMB recommendations to the FDA, Institutional Review Board (IRB), and sponsoring agencies as required by regulations for human subjects' research.

HUMAN SUBJECT ISSUES

Obtaining informed consent of patients resuscitated from OHCA, or from their legally authorized representative (LAR) is difficult. Patients are in an immediate life-threatening situation with a mortality rate before discharge of about 50%. Since study procedures must be initiated as soon as feasible after restoration of flow to ensure its efficacy,^(72, 153) we will seek approval from the FDA and IRB to conduct the study under exception from informed consent (EFIC) for emergency research.(CFR 50(24)) The initiation of study procedures prior to notification and consent will only apply to the application of the study device.

EFIC requires community consultation before study initiation as well as public notification before and after study enrollment. We will conduct a random digit dialing telephone survey to meet this requirement, as we have done previously.^(154, 155) This will be supplemented by multiple outreach efforts (e.g. face-to-face, social media, etc.). Patients and their LAR will be notified of enrollment as soon as feasible, and consent obtained for ongoing participation. We will notify the community of the results of the study upon completion of enrollment.

CO-ENROLLMENT

Until recently, it was unlikely that a patient with a time-sensitive condition such as cardiac arrest would be enrolled in multiple trials due to the paucity of trials of resuscitation interventions.⁽¹⁵⁶⁾ But patients that are treated in the field are transported to receiving hospitals that may participate in trials evaluating other acute interventions.^(1, 157-159) Thus co-enrollment can occur as: a) existing participants in a trial (e.g. cancer) become eligible for a resuscitation trial at the onset of an acute life-threatening illness; b) simultaneous or near simultaneous recruitment to more than one trial; or c) participants in a resuscitation trial become eligible later for enrollment in other trials (e.g. in intensive care setting). The receiving hospital participated in the Resuscitation Outcomes Consortium, National Institutes of Health (NIH)'s Stroke Network, and NIH's Prevention and Early Treatment of Acute Lung Injury (PETAL) network. We are aware of at least one case where conflict over co-enrollment in NIH trials required adjudication by a Dean of Medicine.

We will apply guidelines that we previously proposed for co-enrollment to facilitate co-enrollment in trials if appropriate.⁽¹⁶⁰⁾ There is no regulatory prohibition on co-enrollment in more than one study as long as the timing of the interventions differs and one trial can not affect the outcome of the second trial. Trials of interventions for a variety of clinical conditions have allowed co-enrollment without any reported impact.

REFERENCES

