A standard non-invasive blood pressure cuff (e.g., American Diagnostics Corporation, Hauppauge, NY but any one can be used off the shelf) and disposable plastic clamp (e.g., Medline Industries Incorporated, Mundelein, IL) can be used to apply RIC in patients resuscitated from OHCA via three cycles of 5-mins. inflation to 200 mmHg followed by 5-mins. deflation of a blood pressure cuff on a thigh. The cuff occludes the artery; the clamp maintains pressure in the air bladder of the cuff during the inflation periods. No additional benefit is associated with more than three inflations, or with treatment of more than one limb. Note that no device is approved by the Food and Drug Administration to provide RIC in the United States.

This ED-based study will identify human and other factors that may decrease the ability to implement the autoRIC device in patients with OHCA. The study will also confirm the safety of the device for use in the field. This study will use exception from informed consent for emergency research.

PRIMARY AIM FOR PILOT STUDY

Our primary aim is to evaluate the feasibility of random allocation to active RIC (intervention) versus (vs.) sham RIC (control) quickly upon ED arrival following resuscitation from OHCA. Feasibility will be assessed as attrition, defined as the proportion of randomized subjects who do not remain on allocated therapy for the intended study duration. In the intervention group, this will be defined as lack of completion of three cycles of inflation-deflation; In the control group, this will be defined as crossover to the intervention group. Included will be subjects with spontaneous circulation upon ED arrival after receiving chest compressions by emergency medical services (EMS) providers or defibrillation by laypersons or EMS providers. Excluded will be: ST elevation on first electrocardiogram; written do not attempt resuscitation; pregnant; prisoners; trauma, drowning, or hypothermia etiology of arrest; known dialysis fistula; or limb amputation. Enrolled will be 30 patients. All outcomes will be summarized descriptively. The design of a future trial will be modified based on the results of this study.

PRIMARY HYPOTHESIS FOR PILOT STUDY

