The control group will have a sham package opened at the bedside as soon as feasible after ED arrival. This will be identical in size, weight and appearance as that in the intervention group, but will contain a sham device. Upon identification that the patient has been randomized to the control group, the care team will proceed with all other resuscitative measures as in the the intervention group.

Initial critical care management of the post-cardiac arrest patient has a large influence on neurological recovery and survival.⁽¹⁰⁰⁻¹⁰⁴⁾ Combinations of hospital-based treatments improve outcomes in patients resuscitated from cardiac arrest compared to historical controls.⁽¹⁰⁵⁻¹¹⁰⁾ Moreover, patients transported to a receiving hospital with a coronary catheterization laboratory tended to have better outcomes versus transportation elsewhere.⁽¹¹¹⁾

Differences in initial care may explain some of the differences in survival rates for subjects admitted to different hospitals after resuscitation from cardiac arrest.⁽⁶⁾ Collectively, these studies demonstrate that hospital-based care of those resuscitated from OHCA impacts patient outcomes and potentially modifies the effect of interventions for cardiac arrest. Thus, experts have recommended a standardized approach to try to achieve optimal outcomes after resuscitation from cardiac arrest.⁽¹¹²⁾ According to this method, protocols for hypothermia-related care and other post-resuscitation care will be mandated via investigator agreements, as well as encouraged through periodic continuing education of hospital staff throughout the study period.

Standard post-resuscitation care will include early application and maintenance of IH followed by controlled rewarming, as is current practice at our institution. We will monitor adherence with IH in hospital, and require remediation if adherence does not meet *a priori* performance standards. Two trials that monitored treatment adherence observed improved outcomes with IH vs. no hypothermia after OHCA.^(29, 113) Earlier initiation of IH after hospital arrival is associated with significantly better survival.⁽¹¹⁴⁾ In contrast, IH without documented achievement of a therapeutic temperature range was not associated with benefit among patients resuscitated from in-hospital arrest.⁽¹¹⁵⁾ There is ongoing equipoise related to the duration and targeted temperature range of IH. In practice, most of our patients receive 24 h of IH targeted to 33°C.

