The effectiveness of other components of post-resuscitation care remains unclear because observational studies may overestimate the effects of treatment vs. randomized designs.^(116, 117) Importantly, we will mandate those components of post-resuscitation care likely to be associated with survival benefit and monitor others. Mandated components will include: emergent coronary angiography in patients with VF; timing of prognosis assessment and withdrawal of care; and implantable defibrillator insertion as indicated. Prohibited will be sedation with propofol. Monitored components will include: hemodynamic monitoring and support; seizure prevention and control; insulin therapy and oxygenation.

Intervention Group

The intervention group will have an RIC package opened at the bedside as soon as feasible after ED arrival. This package will be identical in size, weight and appearance as that in the control group, but will contain a manual blood pressure cuff and a clamp. The medical assistant will place the cuff around the left upper arm in the usual manner midway between the shoulder and elbow, inflate the cuff by pumping air from a bulb held in her hand through a tube into the cuff's bladder, then place a clamp on the tube to prevent air from leaking out of the bladder. The left arm is the preferred limb so as to leave the right thigh and wrists available for emergency coronary angiography. The left thigh is an alternative site but application of RIC to the upper extremity may be superior than application to the lower extremity.⁽⁸³⁾ The cuff will be kept inflated for 5 minutes then deflated for 5 minutes by the medical assistant intermittently inflating the cuff and applying the clamp or reversing the procedure. This will be repeated for three cycles (i.e. 35 minutes total—last 5 minutes is deflation). All other resuscitative measures will be the same as the control group.

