All medical assistants who work in the ED of the participating hospital have been trained in how to apply RIC. These individuals completed a minimum of 720 clock hours of training in medical assisting skills to be certified as medical assistants by Washington State before the start of their employment in the ED. As such, their training most closely resembles that of entry level firefighter/emergency medical technicians. Each medical assistant will be required to demonstrate proficiency in application of the active and sham autoRIC device before study enrollment begins. Anyone who is not proficient will receive corrective training then be required to demonstrate proficiency.

Standard post-resuscitation care will be mandated and monitored as in the control group.

MONITORING OF CONCURRENT CARE

Initial critical care management of patients with EC has an influence on subsequent neurological recovery and survival.^(101, 103, 104, 118, 119) Case-control studies have evaluated the effectiveness of combinations of hospital-based treatments in patients resuscitated from cardiac arrest in a variety of settings.^(105-109, 120) All of these studies reported improved outcomes vs. historical controls. As well, greater survival to discharge was associated with greater adherence to recommended hospital-based post-resuscitative care guidelines.⁽¹²¹⁾ Collectively, these studies demonstrate that hospital-based care of patients with OHCA impacts outcomes and may modify the effect of interventions evaluated in a trial. Failure to monitor these elements of care may attenuate the effect of the study treatment.

A summary of use of mandated, monitored and prohibited care processes, without patient outcome, will be provided to hospital providers at least quarterly. If performance deviates from expectations, we will work with hospital providers to address these concerns.

STUDY ASSESSMENTS

Screening and Pretreatment Assessments

There is limited time for screening and pretreatment assessments in this trial because of the acute life-threatening nature of OHCA. Study personnel will screen each OHCA patient transported to the recruiting hospital. Information about patient baseline characteristics and processes of care will be abstracted from the clinical record after enrollment.

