The initial neurological⁽¹²²⁾ and cardiopulmonary status⁽¹²³⁾ upon hospital arrival are important determinants of outcomes after OHCA. Also, the initial degree of cardiopulmonary failure upon hospital arrival is predictive of subsequent development of multi-organ failure. Treating providers will be asked to document neurological status (assessed using the Full Outline of UnResponsiveness [FOUR] score)⁽¹²⁴⁾ and cardiopulmonary dysfunction (assessed using Serial Organ Failure [SOFA] score)⁽¹²⁵⁻¹²⁷⁾ before randomization. These scores are important covariates and will be useful for exploratory secondary analyses.

Documentation of Treatment

This will be assessed as treatment assigned; treatment received; time points used to monitor the time-dependent nature of the intervention including call to 911, sustained restoration of spontaneous circulation (ROSC), initiation of RIC, completion of treatment cycles.

Monitoring for Outcomes

Study staff will review subject's clinical record daily to monitor for outcomes and potential adverse events as well as to monitor use of concomitant treatments.

PRIMARY OUTCOME

Attrition assessed as the proportion of randomized subjects who do not remain on allocated therapy for the intended study duration among subjects randomly allocated. In the intervention group, this will be defined as lack of completion of three cycles of inflation-deflation; In the control group, this will be defined as crossover to the intervention group. Secondary and Exploratory Outcomes

Treatment Success assessed as the proportion of intervention group patients who remain alive and on their allocated therapy for the intended study duration.

Cardiac Function assessed as left ventricular ejection fraction (LVEF) using echocardiograms ordered for clinical indications.

Cardiogenic Shock assessed as systolic BP < 80 mmHg during any 6 h period within 48 h of the index arrest not due to a correctable cause, and treated with pressors or inotropes or placement of a mechanical cardiac assist device (e.g. intra-aortic balloon pump). Cardiogenic shock correlates with survival after resuscitation from cardiac arrest.^(21, 123)

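### Control-arm attrition counts only crossover, so it cannot register a sham that was not applied or was removed early, and the protocol does not say consistently whether the sham is applied

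*Protocol*

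**What the plan says.** **Aim.** Under Primary Aim for Pilot Study, the trial is to "evaluate the feasibility of random allocation to active RIC (intervention) versus (vs.) sham RIC (control) quickly upon ED arrival".

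**Control procedure.** The Control Group section states: "The control group will have a sham package opened at the bedside as soon as feasible after ED arrival". The package matches the active one from the outside "but will contain a sham device", which is not described further. The next step is: "Upon identification that the patient has been randomized to the control group, the care team will proceed with all other resuscitative measures"; the sentence ends by saying that this is as in the intervention group. No placement, duration or removal of the sham is given.

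**Active procedure.** The Intervention Group section follows the same template. The package looks the same outside "but will contain a manual blood pressure cuff and a clamp", and a full application procedure then follows (cuff position, inflation, clamping, three cycles).

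**Training.** The training paragraph that follows the active procedure says: "Each medical assistant will be required to demonstrate proficiency in application of the active and sham autoRIC device".

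**Primary outcome.** Primary Aim and Primary Outcome define attrition in general as the proportion of randomized subjects who do not stay on their allocated therapy for the intended duration. Each arm then has its own rule. In the intervention arm it is failure to complete three cycles. For controls: "In the control group, this will be defined as crossover to the intervention group".

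**Recording.** Documentation of Treatment lists treatment assigned, treatment received and certain time points. The treatment times it names are the start of RIC and the completion of cycles. Treatment Success is defined for the intervention group only.

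**Benchmark.** Primary Hypothesis and Sample Size set attrition at not more than 25%, with 30 patients (15 per group).

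**The concern.** The sections do not fit together. The aim and the training requirement treat the sham as something that is applied. The only description of the control procedure opens the package and moves on.

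The primary outcome then leaves the question unanswered. Its general definition would cover a control patient who did not stay on the sham, but the control-arm rule replaces that with crossover alone. A feasibility trial whose aim names a sham comparator thus has a primary outcome that cannot show whether the sham was delivered.

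There is also an effect on the benchmark. If crossover is rare, controls add almost only zeros to a pooled rate that may be read against 25%. Poor completion in the active arm is then diluted by about half. The protocol says that the design of the future trial will be modified on the basis of these results, so this dilution could carry forward.

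**Working it through.** **Inputs (all from the protocol).** 15 patients per group, 30 in total; benchmark 25%; stated 95% CI half-widths 16.8% overall and 23.7% per group; control attrition = crossover only; active attrition = fewer than three cycles completed.

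**1. The plan's own precision figures.** Exact (Clopper-Pearson) 95% intervals at the first whole-number counts above 25%:
- 8/30: 12.3% to 45.9%, half-width (45.9 − 12.3)/2 = 16.8%.
- 4/15: 7.8% to 55.1%, half-width (55.1 − 7.8)/2 = 23.7%.

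Both stated figures reproduce. The arithmetic is sound; the issue is what is counted.

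**2. Control rate against sham delivery.** Let *c* be the number of controls who cross over and *u* the number whose sham is not applied or is removed early.
- As defined: control attrition = *c*/15. The term *u* does not appear.
- With *c* = 0, every value of *u* from 0 to 15 gives 0/15 = 0%, with an exact 95% upper limit of 21.8%.

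So a control arm in which no sham was applied would report 0%, with an interval lying wholly below 25%.

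**3. Pooled rate.** Let *a* be the number of active-arm failures.
- As defined: pooled = (*a* + *c*)/30. With *c* = 0 this is *a*/30 = ½ × (*a*/15), half the active-arm rate.

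| Active failures | Active-arm rate | Pooled, no crossover |
|---|---|---|
| 4/15 | 26.7% | 4/30 = 13.3% |
| 7/15 | 46.7% | 7/30 = 23.3% |
| 8/15 | 53.3% | 8/30 = 26.7% |

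With no crossover the pooled rate reaches 25% only when active non-completion reaches 50%.

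**4. If sham non-delivery counted.** The protocol gives no rate for it. As an assumption, take 20% to 40% of controls, that is 3 to 6 of 15, with no crossover and no overlap. Pooled = (*a* + *u*)/30:
- *a* = 4: (4 + 3)/30 = 23.3% to (4 + 6)/30 = 33.3%, against 13.3% as defined.
- *a* = 7: (7 + 3)/30 = 33.3% to (7 + 6)/30 = 43.3%, against 23.3% as defined.

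These are illustrations of sensitivity, not forecasts.

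**5. The texts side by side.** The active and control sections share one sequence: package opened, contents stated, other care the same in both arms. The active section puts an application procedure inside that sequence; the control section has none. The training paragraph presupposes one. The protocol therefore gives no duration against which staying on the sham could be judged.

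**The case against.** **The control text does not say that the sham is withheld.** This stands. The full sentence ends by likening care to the intervention group, and the Intervention Group section closes with a mirror statement that plainly does not mean that RIC is omitted. The Control Group section is silent on application; it does not forbid it. Figure 2 is not shown and might say more.

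**The training sentence may be left over from another device.** It refers to the autoRIC device, whereas the device described is a manual cuff and clamp. That is possible, but it is a further reason to reconcile the sections.

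**Sham delivery might be captured elsewhere.** A reader might infer that the feasibility of a sham control is wholly untested. The protocol does not support that. Treatment received is recorded without restriction to one arm, the list of time points is open-ended, and accrual is defined by application of the study device. None of these says that the sham counts, but none excludes it. What is certain is narrower: the primary outcome cannot see it.

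**Crossover is a reasonable control-arm failure.** Yes, and it should stay. Both statements of the rule agree with each other. But crossover alone is narrower than the general definition that introduces it. The protocol also gives precision by group, so reporting by arm would reveal the dilution of active-arm failures; it would not reveal missing shams.

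**Masking.** A reader might infer that the bedside pain readings, taken "at 30 and 60 minutes after randomization in control and intervention group patients", and the withdrawal-of-care outcome are shown to be unmasked. The protocol does not support this. It names no rater for either and promises no masking after the package is opened. It mandates the timing of prognosis assessment and withdrawal of care, and it plans descriptive summaries without comparison.

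**Conclusion.** The concern holds in limited form. The Primary Aim, Control Group and training texts do not agree on whether the sham is applied, and they need reconciling. Independently of how that is settled, sham non-delivery or early removal cannot raise control attrition: 0 to 15 undelivered shams give the same control rate. With no crossover the pooled rate is half the active-arm rate, so 7/15 active failures (47%) read as 7/30 (23%).

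The pooled result assumes equal arms of 15, no crossover, and a 25% benchmark applied to all randomized patients. The protocol does not say whether the benchmark is applied overall or by arm. Nothing in the documents shows that sham non-delivery is likely. The finding is that the primary outcome could not detect it. Because all results are descriptive, what is at stake is the feasibility reading carried into the next trial, not a hypothesis test.

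**What to change.** State in the Control Group section whether the sham is applied, and bring the Primary Aim and the training paragraph into line with that statement.

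- **If it is applied:** describe the sham procedure and its intended duration, record sham start and stop times as is done for RIC, and count a sham not applied or not kept for that duration as control attrition alongside crossover.
- **If it is not applied:** describe the control as an open no-RIC group, remove the sham-application wording from the training paragraph, and set the 25% benchmark against the intervention-arm rate, with control crossover reported separately.

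The cost is protocol wording and, in the first case, two time fields for about 15 controls. The downside is small: control attrition, or the rate set against 25%, may read higher than under the present rule.
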